1.0 Protocol Summary

[figure not shown]
1.1 Synopsis

| | |
|-------------------------|---|
| Title of Study | Post-Exposure Prophylaxis for COVID-19 with Hydroxychloroquine (PEPCOH) |
| Study Objectives | 
Primary:
 
 • Cohort A: Determine whether post-exposure prophylaxis with hydroxychloroquine can prevent COVID-19 in healthcare workers who have been exposed to a known case of COVID-19. • Cohort B: Determine whether post-exposure prophylaxis with hydroxychloroquine can prevent COVID-19 in high-risk individuals who have been exposed to a known case of COVID-19. 
Primary Hypothesis:
 
 • Cohort A: Primary Hypothesis: Hydroxychloroquine will reduce the number of healthcare workers that convert to infected status post-exposure compared with placebo. • Cohort B: Primary Hypothesis: Hydroxychloroquine will reduce the number of high-risk individuals that convert to infected status post-exposure compared with placebo. |
| Study Design | A multi-cohort, prospective, double-blind, randomized, placebo controlled study |
| Study Population | 
Inclusion Criteria:
 
Inclusion Criteria Cohort A:
 
 • ≥ 18 years old • Employee of healthcare organization in South Dakota or Sanford Health employee in any location and with exposure to a person with COVID-19 within the last 5 days 
 ○ Occupational exposure as determined by the participant’s employee health department (i.e. not wearing the proper Personal Protective Equipment (PPE)) ○ Criteria according to Center for Disease Control (CDC) guidelines ○ Community exposure (within 6 feet for at least 15 minutes) • No current symptoms attributable to COVID-19, per HCW report (fever, cough, difficulty breathing, sore throat) • No prior COVID-19 positive diagnosis (eligible if previous testing is negative and meets all other inclusion and exclusion) • Ability to provide informed consent 
Inclusion Criteria – Cohort B
 
 • ≥ 18 years old • High-risk person who had close contact (i.e. within 6 feet for at least 15 minutes) with a COVID-19 positive person within the last 5 days and is a South Dakota resident or high-risk person with close household contact of a COVID-19 positive Sanford employee |

| | |
|--|--|
| | 
 • High-risk person defined by: 
 • Age 18-44 with 2 or more comorbidities listed below • Age 45-79 with any comorbid condition listed below • Age 80 and above (regardless of comorbid conditions) • Co-morbid list 
 ○ Congestive Heart Failure (CHF) ○ Chronic lung disease[‡] ○ Solid organ transplant or immunosuppression* ○ Chronic Kidney Disease or End Stage Renal Disease ○ Diabetes mellitus ○ Cardiovascular disease/Hypertension ○ Smoking/Vaping (currently using or history of using in the past 1 year) ○ Obesity (calculated by height and weight per participant report) ○ Hyperlipidemia ‡Includes any of the following: asthma, chronic obstructive pulmonary disease, emphysema * Defined as an outpatient prescription of greater than 10 mg/day of prednisone or equivalent, use of chemotherapy, or use of immunosuppressive agents for solid organ transplant or for an autoimmune disease. • No current symptoms attributable to COVID-19 • No prior COVID-19 positive diagnosis (eligible if previous testing is negative and meets all other inclusion and exclusion) • Ability to provide informed consent • Confirmed review of concomitant medications (with emphasis on cardiac medications) |
| | 
Exclusion Criteria:
 
Exclusion Criteria Cohort A & B:
 
 • Known allergy to hydroxychloroquine or quinine • Known history of long QT syndrome • Known history of arrhythmia or dysrhythmia • Known current QTc >500 ms • Known G6PD deficiency • Known history of hypoglycemia • Pregnant or Nursing by patient history • Use of any of the following concomitant medications: See Appendix D for Exclusion medication list • Concurrent diagnosis of dermatitis, porphyria, or psoriasis • History of chronic liver disease, including cirrhosis and/or diagnosis of hepatitis (infectious, idiopathic, or immune) • History of chronic kidney disease • Pre-existing retinopathy • Already taking hydroxychloroquine • Any condition or medication in the opinion of the investigator that would prohibit the use of hydroxychloroquine • Enrollment in another clinical with investigational drug or device • Inability to swallow pills • Adults unable to provide informed consent |

| | |
|---------------------------|--|
| | |
| Sample Size | Cohort A n= 1356 Cohort B n= 383 |
| Study Intervention | Hydroxychloroquine vs. Placebo (Vitamin D with calcium) |
| Study Evaluations | Assessments on this study will be completed as outlined in Section 8.3. |
| Study Period | Planned start date: April 2020 Planned accrual start date: April 2020 Planned accrual closure: April 2021 Planned study closure: April 2022 |

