1.2 Schema

1.3 Schedule of Activities (SoA) Cohort A & B

This study consists of screening, enrollment and randomization, treatment, and follow-up. Follow-up will include evaluation of the treatment and subsequent infection, re-infection, adverse events, and long-term sequelae of treatment and/or infection. The detailed schedule of study procedures and assessments with the time intervals is shown in Table 1.

Table 1

| Procedure | Screening & Enrollment | | Treatment / Placebo Phase | | | | | Follow-up ^b | | |
|---|------------------------|----------------------------|---------------------------|-------|--------------------|-------|-------|------------------------|-------------------------------|----------------------|
| | Screening ^a | Enrollment / Randomization | Day 1 | Day 2 | Day 3 ^f | Day 4 | Day 5 | Day 14 (± 1 day) | Day 35 ^c (+3 days) | 12 Months (±30 days) |
| Informed Consent / HIPAA | X | | | | | | | | | |
| Inclusion/Exclusion | X | | | | | | | | | |
| Demographics | X | | | | | | | | | |
| Randomization | | X | | | | | | | | |
| Hydroxychloroquine / Placebo (Vitamin D with calcium) | | | X | X | X | X | X | | | |
| Patient Reported symptoms ^c | | | | | X | | X | X | X | |
| Adverse Event Assessment | | | | | X | | X | X | X | X |
| Outcomes ^d | | | | | | | | X | X | X |

a. Screening must be completed within 48 hours prior to study enrollment

b. Follow-up visits will consist of a phone call to the patient. Hydroxychloroquine and placebo patients will be followed.

c. Includes: patient reported temperature, cough, difficulty breathing, sore throat, chills, muscle pain, headache, new loss of taste or smell, and diarrhea.

d. Did the patient acquire COVID-19?

e. Day 35 should be at least 30 days (+3 days) post last dose of drug.

f. Day 3 and 5 AE assessment via phone call. (window ±1day)

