6.4 Participant Implications

1. If a participant vomits after taking their dose study drug it will be considered a missed dose and not retaken. The participant will resume with the next scheduled dose.
2. If the participant forgets to take a dose, that dose will not be made up and participant will resume with the next scheduled dose.
3. If the participant is unable to start the hydroxychloroquine / vitamin D with calcium in the morning on Day 1 due to delivery timing, the participant is allowed to initiate Day 1 with an evening dose.
4. Participants should have at least 8 hours between doses.

5. Participants will be instructed to inform the study coordinator of any medication changes while on the active phase of the study

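### Eligibility is checked only at screening, up to 48 hours before enrolment, and no rule separates illness that begins before first dose from a post-dose infection

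*Combined protocol and SAP*

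**What the plan says.** **Exposure.** In section 1.1, Cohort A requires "exposure to a person with COVID-19 within the last 5 days". Cohort B requires close contact "with a COVID-19 positive person within the last 5 days and is a South Dakota resident", or being a "high-risk person with close household contact of a COVID-19 positive Sanford employee". That second branch has no time limit of its own as worded. Neither cohort's criterion states the date from which the 5 days are counted back.

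**Infection status at entry.** Cohort A requires "No current symptoms attributable to COVID-19, per HCW report", and Cohort B has the same requirement without the reporting clause. Both cohorts require "No prior COVID-19 positive diagnosis (eligible if previous testing is negative" and otherwise eligible). Neither Table 1 nor the screening list in 8.1.1 includes a baseline SARS-CoV-2 test.

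**Timing.** Table 1 marks Inclusion/Exclusion under Screening only. Footnote a reads "Screening must be completed within 48 hours prior to study enrollment", and 8.1.1 repeats the limit. Under 8.1.5 the investigator or a licensed designee reviews the eligibility source document, and the participant is then enrolled and randomised. Section 6.4 provides that, if a morning start is not possible "due to delivery timing, the participant is allowed to initiate Day 1 with an evening dose". No maximum interval from randomisation to first dose is given. Patient-reported symptoms are first scheduled at Day 3.

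**Outcome.** Section 3.2 speaks of conversion after exposure. Table 1 records at Day 14, Day 35 and 12 months whether the participant acquired COVID-19. Section 9.3 compares proportions by Fisher's exact test, states no analysis set or onset-date rule, and leaves detail to a SAP that is not in the documents.

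**The concern.** A prophylaxis trial needs to know that participants were free of the disease when the drug could first act. Here the last scheduled check is at screening. If the 5 days also run to screening, the last qualifying exposure may be 5 + 2 = 7 days before enrolment with every rule met. Some participants may become symptomatic in that interval.

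Study drug not yet taken cannot prevent illness that has already begun. Such events fall equally, in expectation, on both arms and pull the relative risk toward 1. The sample size in 9.2 assumes a 50% reduction over all counted infections, with no allowance for this. A null result could then reflect either an ineffective drug or late dosing, and the data needed to tell them apart (contact dates, first-dose time, symptoms before first dose) are not specified for collection.

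**Working it through.** **1. Reproduce the plan's sample size.** Inputs from 9.2 and 9.4: 10% v 5% (Cohort A), 30% v 15% (Cohort B), α = 0.0492, power 90%, 10% dropout. Sidedness is not stated; two-sided reproduces the figures. Exact unconditional power of the two-sided Fisher test is 90.02% at 610 per arm and 90.04% at 172 per arm. Dropout: 1220/0.9 = 1355.6, giving 1356; 344/0.9 = 382.2, giving 383. The stated sizes are correct for their assumptions.

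**2. How many infections could show onset before dosing?** The documents give no incubation figure, so this is assumed: log-normal incubation with distribution function F, median 4–7 days, log-SD 0.4–0.5, and a single exposure. For screening on day u and a gap g from screening to first dose, the share of infections still symptom-free at screening that have onset before dosing is

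[F(u+g) − F(u)] / [1 − F(u)].

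Example with median 5, log-SD 0.4, u = 5 and g = 2: F(5) = 0.50; F(7) = Φ(ln 1.4 / 0.4) = Φ(0.841) = 0.80; share = 0.30/0.50 = 60%. Over the assumed range this extreme case gives 33–72%. For screening on day 1 with the same gap it gives 2–28%.

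Screening would not all fall on day 5. With screening spread evenly over days 0–5, the share is ∫[F(u+g) − F(u)]du / ∫[1 − F(u)]du, integrated from 0 to 5:

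| Gap, screening to first dose | Share with onset before dosing |
|---|---|
| 12 hours | about 2–10% |
| 24 hours | about 6–20% |
| 48 hours | about 15–43% |

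At each gap the low end is median 7 and the high end median 4, both at log-SD 0.4.

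**3. Effect on power.** Let f be the share of control-arm events that precede dosing, with the planned 50% reduction applying to the rest. Observed RR = f + 0.5(1 − f); for example, f = 0.2 gives 0.2 + 0.4 = 0.60. Treated-arm rate = RR × control rate. Exact Fisher power at 610 and 172 per arm, α = 0.0492:

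| f | RR | Treated rate A / B | Power A | Power B |
|---|---|---|---|---|
| 0 | 0.50 | 5.0% / 15.0% | 90.0% | 90.0% |
| 10% | 0.55 | 5.5% / 16.5% | 81.4% | 81.7% |
| 20% | 0.60 | 6.0% / 18.0% | 69.8% | 70.4% |
| 30% | 0.65 | 6.5% / 19.5% | 56.4% | 57.1% |

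**4. Linking steps 2 and 3.** The values of f are illustrative. The 10% row lies within the 24-hour range, 20% is at its upper end, and 30% is reached only in the 48-hour range. Step 2 equals f only if every counted event is a symptomatic infection from the qualifying exposure. Infections from later exposures, counted to Day 35 or 12 months, or found without symptoms would lower it.

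**The case against.** The best defence is that the actual workflow is quick and the gap largely theoretical. Section 8.1.2 describes consent by telephone with 1–4 hours to read, 8.1.5 describes real-time notice of randomisation, and 48 hours is a ceiling. The criteria are worded in the present tense and could be read as applying at enrolment. This stands in part: the short-gap rows are plausible. But Table 1 schedules no renewed check, so the present-tense reading depends on each site's practice.

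Several stronger readings are tempting and should be resisted.

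- *Early onset goes entirely unseen.* Section 8.3.1 collects adverse events from consent, and section 8.3 defines them to include any abnormal symptom. Onset may be captured, though the first scheduled assessment is Day 3 and nothing ties the record to eligibility or outcome.
- *Delivery adds days.* Section 6.4 documents only a shift from morning to evening of Day 1. A longer delay is not excluded, but it is not shown.
- *The plan declares pre-dose illness a treatment failure.* No sentence says so. It is inferred from an undated outcome question and the absence of an exclusion rule, with detail deferred to a SAP.
- *A third to nearly three quarters of infections would precede dosing.* That is the case where everyone is screened on day 5 and waits the full 48 hours.
- *The window should run from first contact, because continuing household contact always satisfies it.* This is true of the time criterion only; symptoms and a prior positive diagnosis still exclude. Sections 2.1 and 2.2 make progression to symptomatic disease and early pre-emptive therapy part of the rationale, so incubating infection is within the target. Counting from first contact would remove long-exposed household contacts from Cohort B, which is a debatable trade-off and not a correction.

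**Conclusion.** The point holds in a limited form. As written, a person whose symptoms begin between screening and first dose can be randomised, and no rule separates that event from a post-dose infection. Because allocation is 1:1 and the drug has not been taken, the effect is balanced dilution. It costs power and makes a null result hard to interpret, but it does not raise the type I error or create a spurious benefit.

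The size is conditional. If 10–30% of control events precede dosing, power falls from 90% to 81–56% in Cohort A and 82–57% in Cohort B. Whether f reaches those values rests on the assumed incubation distribution, a single exposure, and the actual gap to first dose, none of which the documents supply. With gaps of 12 hours the loss would be small; with routine use of the full 48 hours it would be serious. The sample-size arithmetic itself is not in dispute. The change is worth making because it is cheap and because dates that were never collected cannot be recovered later by a SAP.

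**What to change.** 1. In Table 1, add an X under Enrollment/Randomization for Inclusion/Exclusion and for patient-reported symptoms, re-asked on that day's call.
2. In 1.1, state that the 5-day window and the symptom-free criterion apply at randomisation, and that the window also covers the branch for household contacts of Sanford employees. Do not redefine the window to run from first contact.
3. Record dates of first and last contact with the index case, date and time of first dose, and any symptoms before it. The pill diary in 6.7 can hold the last two.
4. In 9.3, keep all randomised participants in the main analysis. Prespecify one supportive analysis that omits events with onset or positive specimen before first dose, identified blind to arm.

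The cost is one repeated telephone question, a few data fields, one extra analysis and a few more screen failures. No dose or treatment rule changes.

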6.2.7. Contraindications

Use of hydroxychloroquine sulfate is contraindicated in patients with known hypersensitivity to 4-aminoquinoline compounds. Use with

caution in patients with alcoholism, hepatic/renal dysfunction, glucose-6-phosphate dehydrogenase (G-6-PD) deficiency, gastrointestinal, neurological, or blood disorders. A dose reduction may be required.

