CONTRAINDICATIONS: Use of hydroxychloroquine sulfate tablets are contraindicated in patients with known hypersensitivity to 4-aminoquinoline compounds.

WARNINGS: Resistant Strains of Malaria: Hydroxychloroquine sulfate tablets are not effective against chloroquine-resistant strains of *P. falciparum* (see CLINICAL PHARMACOLOGY: Microbiology).

Ocular: Irreversible retinal damage has been observed in some patients who had received hydroxychloroquine sulfate. Significant risk factors for retinal damage include daily doses of hydroxychloroquine sulfate greater than 6.5 mg/kg (5 mg/kg base) of actual body weight, durations of use greater than five years, subnormal glomerular filtration, use of some concomitant drug products such as tamoxifen citrate and concurrent macular disease.

A baseline ocular examination is recommended within the first year of starting hydroxychloroquine sulfate tablets. The baseline exam should include: best corrected distance visual acuity (BCVA), an automated threshold visual field (VF) of the central 10 degrees (with retesting if an abnormality is noted), and spectral domain ocular coherence tomography (SD-OCT).

For individuals with significant risk factors (daily dose of hydroxychloroquine sulfate greater than 5.0 mg/kg base of actual body weight, subnormal glomerular filtration, use of tamoxifen citrate or concurrent macular disease) monitoring should include annual examinations which include BCVA, VF and SD-OCT. For individuals without significant risk factors, annual exams can usually be deferred until five years of treatment.

In individuals of Asian descent, retinal toxicity may first be noticed outside the macula. In patients of Asian descent, it is recommended that visual field testing be performed in the central 24 degrees instead of the central 10 degrees.

It is recommended that hydroxychloroquine be discontinued if ocular toxicity is suspected and the patient should be closely observed given

that retinal changes (and visual disturbances) may progress even after cessation of therapy.

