Hypoglycemia: Hydroxychloroquine sulfate tablets have been shown to cause severe hypoglycemia including loss of consciousness that could be life-threatening in patients treated with or without antidiabetic medications (see DRUG INTERACTIONS and ADVERSE REACTIONS). Patients treated with hydroxychloroquine sulfate tablets should be warned about the risk of hypoglycemia and the associated clinical signs and symptoms. Patients presenting with clinical symptoms suggestive of hypoglycemia during treatment with hydroxychloroquine sulfate tablets should have their blood glucose checked and treatment reviewed as necessary.

PRECAUTIONS: General: Use with caution in patients with gastrointestinal, neurological, or blood disorders, and in those with a sensitivity to quinoline.

Hepatic/Renal Disease: Antimalarial compounds should be used with caution in patients with hepatic disease or alcoholism or in conjunction with known hepatotoxic drugs. A reduction in dosage may be necessary in patients with hepatic or renal disease, as well as in those taking medicines known to affect these organs.

Hematologic Effects/Laboratory Tests: Antimalarial compounds should be used with caution in patients with hepatic disease or alcoholism or in conjunction with known hepatotoxic drugs. Periodic blood cell counts should be performed if patients are given prolonged therapy. If any severe blood disorder such as aplastic anemia, agranulocytosis, leukopenia, or thrombocytopenia, appears which is not attributable to the disease under treatment, consider discontinuation of hydroxychloroquine sulfate tablets.

Hydroxychloroquine sulfate tablets should be administered with caution in patients having glucose-6-phosphate dehydrogenase (G-6-PD) deficiency.

Dermatologic Effects: Dermatologic reactions to hydroxychloroquine sulfate tablets may occur and, therefore, proper care should be exercised when it is administered to any patient receiving a drug with a significant tendency to produce dermatitis.

Drug Interactions: Digoxin: Concomitant hydroxychloroquine sulfate tablets and digoxin therapy may result in increased serum digoxin levels; serum digoxin levels should be closely monitored in patients receiving combined therapy.

Insulin or Antidiabetic Drugs: As hydroxychloroquine sulfate tablets may enhance the effects of a hypoglycemic treatment, a decrease in doses of insulin or antidiabetic drugs may be required.

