Drugs that Prolong QT Interval and Other Arrhythmogenic Drugs: Hydroxychloroquine sulfate tablets prolong the QT interval and should not be administered with other drugs that have the potential to induce cardiac arrhythmias. Also, there may be an increased risk of inducing ventricular arrhythmias if hydroxychloroquine sulfate tablets are used concomitantly with other arrhythmogenic drugs.

Mefloquine and Other Drugs Known to Lower the Convulsive Threshold: Hydroxychloroquine sulfate tablets can lower the convulsive threshold. Co-administration of hydroxychloroquine sulfate tablets with other antimalarials known to lower the convulsion threshold (e.g., mefloquine) may increase the risk of convulsions.

Antiepileptic: The activity of antiepileptic drugs might be impaired if co-administered with hydroxychloroquine sulfate tablets.

Methotrexate: Combined use of methotrexate with hydroxychloroquine sulfate tablets have not been studied and may increase the incidence of adverse effects.

Cyclosporin: An increased plasma cyclosporin level was reported when cyclosporin and hydroxychloroquine sulfate tablets were co-administered.

The following interactions have been observed on treatment with the structurally related substance chloroquine phosphate, and therefore cannot be ruled out for hydroxychloroquine.

Praziquantel: Chloroquine has been reported to reduce the bioavailability of praziquantel.

Antacids and Kaolin: Antacids and kaolin can reduce absorption of chloroquine; an interval of at least 4 hours between intake of these agents and chloroquine should be observed.

Cimetidine: Cimetidine can inhibit the metabolism of chloroquine, increasing its plasma level. Concomitant use of cimetidine should be avoided.

Ampicillin: In a study of healthy volunteers, chloroquine significantly reduced the bioavailability of ampicillin.

Information for Patients: Patients should be informed of the early signs and symptoms of toxicity such as rash or visual changes. Patients must see their physicians promptly in case of the appearance of these or of any unusual effects. Periodic laboratory tests may be recommended in some patients. Patients should be fully informed of the potential risks of the use of hydroxychloroquine sulfate tablets, especially in pregnancy and in children.

Carcinogenesis, Mutagenesis, Impairment of Fertility: Long-term studies in animals have not been conducted to evaluate the carcinogenic potential of hydroxychloroquine sulfate tablets.

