The mutagenic potential of hydroxychloroquine was not evaluated. However, chloroquine has been shown to be a catalytic inhibitor of DNA repair enzymes (topoisomerase II) and to produce weak genotoxic effects through this mode of action.

Pregnancy - Teratogenic Effects: Human pregnancies resulting in live births have been reported in the literature and no increase in the rate of birth defects has been demonstrated. Embryonic deaths and malformations of anophthalmia and microphthalmia in the offspring have been reported when pregnant rats received large doses of chloroquine.

Nursing Mothers: Caution should be exercised when administering hydroxychloroquine sulfate tablets to nursing women. It has been demonstrated that hydroxychloroquine administered to nursing women is excreted in human milk and it is known that infants are extremely sensitive to the toxic effects of 4-aminoquinolines.

Pediatric Use: Safety and efficacy have not been established in the chronic use of hydroxychloroquine sulfate tablets for systemic lupus erythematosus and juvenile idiopathic arthritis in children. Children are especially sensitive to the 4-aminoquinoline compounds. Most reported fatalities followed the accidental ingestion of chloroquine, sometimes in small doses (0.75 g or 1 g in one 3-year-old child). Patients should be strongly warned to keep these drugs out of the reach of children (see OVERDOSAGE).

Geriatric Use: Clinical studies of hydroxychloroquine sulfate tablets did not include sufficient numbers of subjects aged 65 and over to determine whether they respond differently from younger subjects. However, this drug is known to be substantially excreted by the kidney, and the risk of toxic reactions to this drug may be greater in patients with impaired renal function. Because elderly patients are more likely to have decreased renal function, care should be taken in dose selection and it may be useful to monitor renal function.

ADVERSE REACTIONS: The following adverse reactions have been identified during post-approval use of hydroxychloroquine sulfate tablets or other 4-aminoquinoline compounds. Because these reactions are reported voluntarily from a population of uncertain size, it is not always possible to reliably estimate their frequency or establish a causal relationship to drug exposure.

Blood and Lymphatic System Disorders: Bone marrow failure, anemia, aplastic anemia, agranulocytosis, leukopenia, and

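### The named allergy exclusion does not cover the drug's stated contraindication, so excluding a person hypersensitive only to chloroquine rests on investigator judgement

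*Combined protocol and SAP*

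**What the plan says.** Section 1.1 holds the operative exclusion list for both cohorts; section 5.2 (Exclusion) only refers back to it. Its one allergy item is "Known allergy to hydroxychloroquine or quinine". The same list ends with general items, among them "Any condition or medication in the opinion of the investigator that would prohibit the use of hydroxychloroquine".

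Section 6.2.7 states: "Use of hydroxychloroquine sulfate is contraindicated in patients with known hypersensitivity to 4-aminoquinoline compounds". The package insert in Appendix C agrees: "Use of hydroxychloroquine sulfate tablets are contraindicated in patients with known hypersensitivity to 4-aminoquinoline compounds". Neither place gives any other contraindication for hydroxychloroquine. The insert's general precautions also advise caution in certain disorders "and in those with a sensitivity to quinoline".

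On enrolment, section 8.1.1 lists medical history among the screening activities. Sections 8.1.3 and 8.1.5 have the site principal investigator or a licensed designee (nurse, nurse practitioner, pharmacist or physician) review the criteria before randomisation.

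**The concern.** A contraindication that a protocol states for its own study drug would normally appear as a named eligibility criterion, because the named criteria are what screening staff check. Here it was carried over only in part. Several conditions for which the drug text gives only a caution or warning did become named exclusions: G6PD deficiency, psoriasis, porphyria, hypoglycemia and chronic liver disease. The one contraindication is represented by two drug names that do not span the class.

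At stake is the safety of a few participants. Consent is handled by telephone and email (section 8.1.2), section 6.4 speaks of study drug being delivered, and the first scheduled adverse event contact is a telephone call on Day 3, within a day either way (Table 1). A reaction history that screening does not ask about by name may not surface before dosing starts.

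**Working it through.** No figure in the plan depends on this point, so the check is a comparison of texts.

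1. **Named criterion (section 1.1).** It covers allergy to hydroxychloroquine and to quinine. It names neither chloroquine nor the 4-aminoquinoline class.

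2. **Contraindication (section 6.2.7; Appendix C, Contraindications).** Both are class-wide, and they agree with each other.

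3. **Is chloroquine in that class on the documents' own terms?** The insert's paediatric text reads "Children are especially sensitive to the 4-aminoquinoline compounds. Most reported fatalities followed the accidental ingestion of chloroquine", which makes sense only if chloroquine is one of those compounds. The drug interaction text calls it the "structurally related substance chloroquine phosphate, and therefore cannot be ruled out for hydroxychloroquine". Section 6.2.1 lists 4-aminoquinoline among hydroxychloroquine's other names. Membership is implied rather than stated, but the implication is clear.

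4. **Does another named criterion close the gap?** Sections 5.1 and 5.2 add nothing to the synopsis. Appendix D lists chloroquine, but section 1.1 applies that appendix to concomitant medication. It catches current use, not a past reaction.

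5. **Does an unnamed criterion close it?** The investigator-opinion clause can. A hypersensitivity that the protocol itself calls a contraindication is a natural case for it. The clause works only if the reaction comes to light and the reviewer links chloroquine to the class.

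6. **Exposure before the first scheduled safety call.** Section 6.1 schedules 2 × 2 = 4 tablets on Day 1 and 1 × 2 = 2 tablets on each of Days 2 to 5, for 4 + 4 × 2 = 12 in all. With a morning start on Day 1, 4 + 2 = 6 of 12 tablets are due by the end of Day 2. If the call falls on Day 4, the end of its window, 4 + 2 + 2 = 8 are due by the end of Day 3. An evening start, which section 6.4 allows, may lower these counts.

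Steps 1 to 5 give the result: a person hypersensitive to chloroquine alone meets every named criterion, and exclusion depends on one discretionary clause.

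**The case against.** The strongest reply is that such a person would be excluded anyway. The discretionary clause sits in the same list, medical history is part of screening, and a licensed reviewer must confirm eligibility before randomisation. That stands to this extent: a reader might infer that the protocol simply lets a person with a known contraindication be randomised and dosed, and the documents do not support so flat a statement. What remains is that this safeguard depends on recognition case by case, by reviewers of differing professions, at a lead institution and possibly at other institutions (section 4.1).

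A reader might also call the exclusion narrower than the contraindication. That is not shown. The exclusion names quinine, which the contraindication does not, and nothing in the documents says that quinine is a 4-aminoquinoline. On this record the two wordings may differ in both directions. The insert's mention of quinoline sensitivity is a caution, so it adds no second contradiction.

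Finally, a reader might link this to the line in section 6.2.7, "A dose reduction may be required", and infer a further conflict with the fixed course in section 6.1. That is a separate and weaker matter. The wording is permissive, and the insert ties dose reduction to hepatic or renal disease and to medicines affecting those organs, while section 1.1 already excludes chronic liver and chronic kidney disease. It forms no part of this point.

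**Conclusion.** The point holds as a specific mismatch between an operative eligibility rule and the only contraindication the protocol states for hydroxychloroquine. It rests on two things: the insert's implied placing of chloroquine among the 4-aminoquinolines, and the absence of any other named criterion for a past reaction. The screening checklist is not among the documents, so whether it asks more widely cannot be judged.

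The documents do not say how many people are affected; that the number is small is an assumption. Planned enrolment would not measure it, since it counts everyone enrolled and not those with such a history. Sample size, alpha and power do not change. The issue warrants correction because it concerns safety and is cheap to remove, but it does not threaten the trial's conclusions.

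**What to change.** Reconcile the allergy exclusion in section 1.1 with section 6.2.7 and the Contraindications text in Appendix C, so that the criterion and the contraindication cover the same compounds. The reconciliation should also settle how quinine, which only the exclusion names, relates to the contraindication. The medical lead decides the wording; this review takes no position on which text is clinically right. Carry the agreed wording into the inclusion/exclusion source document used at screening, so that the question is put to every candidate by name.

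The cost is about one line in the synopsis and a matching line in the screening form, with negligible effect on accrual and no change to the statistical sections.
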